#### Interventions to be tested:

The interventions proposed for this study are in current clinical use. Both coronal and root surface tooth decay lesions will be treated. The two evidence-based strategies in older adults will be compared as follows:

##### **Arm 1 (N=275 participants): A “simple medical strategy” consisting of SDF**

The treatment will be bi-annual application (at baseline and 26 weeks) of topical 38% silver diamine fluoride (Advantage Arrest, Elevate Oral Care LLC., West Palm Beach, FL) following manufacturer's instructions and guidelines published by UCSF.

##### **Arm 2 (N=275 participants): A “typical dental strategy” consisting of ART + FV**

Atraumatic Restorative Treatment (ART) will be a modification of the approach used by Lo and colleagues (2006), and the cavity restored at baseline with resin reinforced glass-ionomer cement (GIC) (GC Corporation, Japan).

Participants in this arm will also receive biannual topical fluoride varnish application (FluoriMax, Elevate) according to manufacturer's instructions.

#### **Modifications Made Due to COVID-19**

*Due to COVID-19 restrictions which prevented outside visitors/providers at the housing sites, recruitment will take longer than the anticipated 24 months. Additionally, approximately 40 enrolled individuals did not complete the 26 week visit/second dose of treatment. We will therefore increase the total number of enrolled participants by 40. We are also adding four additional housing facilities to the study to address some delays in recruitment due to the COVID-19 pandemic. These four sites are managed by National Church Residences.*

---

*The additional 4 sites will also be randomized to Arm 1 and Arm 2 for a total of 13 sites in each arm.*

## 5 STUDY ENROLLMENT AND WITHDRAWAL

The *original* 22 housing facilities have a total of 3749 tenants 62 years and older, therefore, we will approach 1368 participants, out of whom 958 will be screened for cavities to obtain the target sample of 550 older adults (approx. 25/housing facility) who have at least one natural tooth. Only individuals with severe medical, cognitive or motor impairments will be excluded. Individuals living independently (our study population) will likely not have severe impairments. Severe medical and motor impairments preventing enrollment will be those which would prevent the individual from completing the dental screening. Severe cognitive impairment will be determined through the consent process. If an individual is unable to explain back to the person obtaining consent what the study involves and what they will do, they will not be consented. Recruitment efforts for the main trial will take place over a two-year period. The study staff will approach tenants at various venues and inquire if they are completely edentulous to check study inclusion/exclusion criteria. Following are the estimates based on our prior study: 73% had at least one tooth; 70% providing consent; 58% with untreated caries. We expect a target of 550 participants to be randomized to the two arms.

The recruitment for all housing sites will follow a 2-stage process: (1) all participants consented will participate in the dental screening; (2) participants found to have non-urgent cavities at the screening and who fulfill the inclusion criteria will be enrolled into the clinical trial.

### 5.1 Subject *Initial* Inclusion Criteria

In the first stage of the enrollment process, an individual must meet all of the following criteria:

- Provide signed and dated informed consent form
- Willing to comply with all study procedures and be available for the duration of the study (1 year)
- Male or female, aged 62 years or older
- Live in a participating older adult housing facility

In the second stage of enrollment process, additional inclusion criteria for continuation and participation in the RCT is based on the dental screening:

- Have at least one untreated root or coronal caries lesion on any permanent tooth with an International Caries Detection and Assessment System (ICDAS) II active lesion score of 3 or greater (localized enamel cavity to extensive cavity).

### 5.2 Subject Exclusion Criteria

Following the dental screening, further exclusion criteria for non-eligibility to participate in the RCT include:

- Sensitivity to silver or other heavy-metal ions
- Those with ulcerative gingivitis or stomatitis which prevents them from receiving study treatment
- Serious life-threatening medical disease

### 5.3 Strategies for Recruitment and Retention

We will use prior successful strategies in recruiting and also solicit input from our stakeholders. Strategies that will be used are as follows: Service coordinators at all 22 facilities will serve as site liaisons. The study PI/project manager will provide the service coordinators with an introductory letter/flyer containing study information to be given to tenants and to be posted in public areas of the facility. Service coordinators will first arrange an informational meeting (study dentist will give a talk on the interventions as suggested by our stakeholders), and will arrange a second recruitment meeting for study staff to present information regarding the study at scheduled group events (e.g. tenant meetings, health fairs). For planning purposes, service coordinators will have a sign-up sheet for those interested in the sessions. Study staff will schedule those who are interested and meet the inclusion criteria for one-on-one sessions at the housing facility to obtain informed consent and collect baseline survey data. Baseline dental exam and treatment appointments will then be scheduled at each facility according to a designated exam day(s) for each facility, which will occur approximately 1-2 weeks following consent and baseline data collection. Six and twelve month dental exams/treatment and one-on-one interviews for follow-up survey completion for each time point will also occur at the housing facility where participants reside

Retention strategies for participants will include:

- Participants will be given promotional items (i.e. pens, magnets) with the study logo and contact phone number at recruitment.
- Alternate contact information for family/friends that may be able to reach the participant if primary contact information becomes invalid will be obtained at recruitment.
- Annual birthday/holiday cards will be sent to participants to maintain contact.
- Newsletters will be sent twice a year with updates on the study's progress (i.e. recruitment), and a reminder to update their contact information (by phone or mail).
- Assistance from service coordinators or other facility staff will also be solicited for hard to reach/contact participants.
- *Due to COVID-19 delays, an additional 4 housing sites are being added to the study to accelerate recruitment.*

## 5.4 Treatment Assignment Procedures

### 5.4.1 Randomization Procedures (RQ-2)

Randomization is at the level of the cluster (housing facility) for logistical efficiency. This will greatly reduce the potential for error that could otherwise occur with people at the same site assigned to different treatments. Furthermore, keeping the same treatment at each site reduces chances of 'contamination' (i.e. participant discussing their treatment with others). Additionally, stratified cluster randomization will be used, i.e. a block (constrained) randomization approach in which balance over treatments is assured for 2 key cluster-level (stratification) variables, namely facility size (>100 versus ≤100 residents), and geographic location (Cuyahoga County vs other). The project statistician, [name] will generate the randomization scheme for the 22 + 4 additional housing facilities. While the randomization is at the housing level, the study objectives, interventions and primary outcomes all pertain to the individual level (RC-1).

### 5.4.2 Masking Procedures (IR-6)

We will attempt blinding of participants to the study group, but this may not be possible due to SDF color change.

The hygienists will be unaware of the treatment assignment when they go to their respective housing facilities. For all treatment visits, assessments will be conducted prior to the intervention delivery.

Two hygienists will go to the housing facility randomized to the SDF arm and the other two will go to the ART + FV arm. The baseline treatment to be applied will be revealed only after the baseline caries exam has been completed. At the 6 month follow-up visit, the two hygienists that applied SDF will now go to the facilities randomized to the ART + FV facilities and vice-versa to conduct the 6-month follow up caries assessment exam and treatment. We will follow similarly for the 12-month follow-up visit. By this strategy, we will make sure that potential bias of the hygienist evaluating their own work is minimized. Additionally, periodically we will check for the quality of the assessment data by [name] randomly examining 20% of the participants.

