## PROTOCOL SUMMARY

Title:	Reducing Oral Health Disparities of Older Adults: Comparative Effectiveness of 2 Treatments
Précis:	The study is a cluster randomized clinical trial (RCT) to be conducted in 22 publicly subsidized housing facilities/sites (HUD Section 202) and other low-income housing voucher programs in NE Ohio. The facilities will be randomized to 2 arms: Arm 1 (11 sites) – Participants will receive biannual silver diamine fluoride (SDF) versus Arm 2 (11 sites): Participants will receive atraumatic restorative treatment (ART) with glass ionomer cement (GIC) + biannual fluoride varnish (FV) application. A total of 550 participants (Arm 1: 275, Arm 2: 275) will be followed for one year.
Objectives:	
Primary: To compare the effectiveness of two evidence-based strategies, a “simple medical” strategy of topical application of SDF versus a “typical dental” strategy consisting of ART + FV given to older adults 62 and older to address (1) participant reported outcomes including tooth pain and hypersensitivity; and (2) clinical outcomes (caries arrest).
 
Secondary: To assess (1) participant reported outcomes (oral health quality of life, safety, and patient satisfaction); and (2) clinical outcomes (prevention of new decay).

Population:	
Population information: sample size = 550 older adults to be randomized; participants aged <math>\geq</math> 62 years will be recruited from 22 subsidized housing facilities in NE Ohio, and will be randomized if they have at least one untreated active root or coronal carious lesion, and are willing to be in the study for 1 year. The socio-demographics of this population is expected to be a mean age of 74 years, 76% female, 51% Caucasian, 45% African-American, 2% Hispanic, and 2% other groups, 83% with two or more medical conditions.
 
Due to COVID-19 restrictions which prevented outside visitors/providers at the housing sites, approximately 40 enrolled individuals did not complete the 26 week visit/second dose of treatment. We will therefore increase the total number of enrolled participants by 40.

Phase:	III
Number of Sites:	22 independent living facilities for older adults, plus an additional 11 housing facilities to address some delays in recruitment due to the COVID-19 pandemic.

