### **6.8 Procedures for Training Interventionists and Monitoring Intervention Fidelity**

The study interventionists (dental hygienists) will receive didactic and clinical instruction on administration of the clinical interventions. The hygienists will undergo a two-day training and calibration exercise with extracted teeth and applying the intervention on patients. The didactic instruction will include required reading, viewing of technique videos, and laboratory and clinical practice. The supervised laboratory practice will use extracted teeth in which there are natural or instructor created cavities. The clinical application will be practiced on at least one patient.

To be certified, the study interventionist must demonstrate mastery. For ART and FV application the trainee will complete a written or oral exam on procedures (from set up to cleanup); Complete no less than 8 ART on the lab bench on extracted teeth; Complete no less than 3 ART on an older adult patient with cavities; Complete at least one FV treatment on the same patient. For SDF the trainee will complete a written or oral exam on procedures; complete at least 1 treatment on an extracted tooth; complete at least 1 treatment on an older adult patient. During the actual intervention visits to the housing facility, the study dentist will be present to supervise the hygienists to make sure that the study treatment were delivered per protocol. If there is a problem with the delivery of the treatment or adherence to protocol then the

---

interventionists will be given corrective training. *For 52 week follow-up visits, where treatment will not be delivered, the study dentist may not be present.*

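### As written, Section 5.4.2 gives each arm its own examiner pair at week 52, so caries arrest and new decay would be confounded with who scored them

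*Combined protocol and SAP*

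**What the plan says.** All the allocation rules are in Section 5.4.2.

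- Baseline: "Two hygienists will go to the housing facility randomized to the SDF arm and the other two" go to the ART+FV arm. Treatment is revealed only after the baseline caries exam.
- 6 months, exam and treatment: "the two hygienists that applied SDF will now go to the facilities randomized to the ART + FV facilities and vice-versa".
- 12 months: "We will follow similarly for the 12-month follow-up visit".
- Masking: "The hygienists will be unaware of the treatment assignment when they go to their respective housing facilities".
- Quality check: one named person is "randomly examining 20% of the participants" from time to time. The visit is not specified.

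The stated purpose of the swap is to keep hygienists from scoring their own work. Under Section 7.3 hygienists do the week-52 exam for arrest and new decay. Section 6.8 adds that at those visits, "where treatment will not be delivered, the study dentist may not be present". Section 11.4 tests arrest with a z-based 95% CI against a margin of 0.09, then fits GEE models with treatment and prognostic variables. It names no examiner term and no analytic use of the re-examinations.

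**The concern.** Swapping whole arms between pairs removes self-assessment at 6 months, but it leaves each arm with a single examiner pair at each visit. Arrest is scored by visual and tactile examination. If the two pairs differ at all in how readily they call a lesion arrested, that difference adds directly to the SDF minus ART+FV contrast, and no planned analysis would show it. Person-level arrest requires every lesion to be arrested (Section 11.2), so a small per-lesion difference can grow.

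The section also contradicts itself: a pair that serves one arm knows the arm of its next site once the first treatment has been revealed.

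**Working it through.** **1. Can pair be separated from arm?** The 12-month sentence does not say whether pairs swap back or stay swapped. I checked both.

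- Week 52 only (intercept, arm, pair): rank 2 of 3. Fully aliased.
- Weeks 26 and 52 with arm, visit, arm-by-visit and pair: rank 4 of 5. Aliased.
- Three visits with categorical time: rank 6 of 7. Aliased.
- Three visits with linear time: rank 5 of 5. Estimable in principle, but no such term is planned. Treated lesions are active at entry and new decay is defined against the previous exam (Section 8.1.1), so neither outcome has an informative baseline value.

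The ranks are the same under both readings of the 12-month sentence.

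**2. Reproducing the plan's arrest power.** Inputs from Section 11.2: 275 per arm in 11 sites, 25 per site, 15% dropout, ICC 0.01, 90% arrest in both arms, margin 0.09, one-sided alpha 0.025.

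- n = 275 × 0.85 = 233.75; m = 25 × 0.85 = 21.25
- Design effect = 1 + (21.25 − 1) × 0.01 = 1.2025; effective n = 194.4 per arm
- SE = √(2 × 0.9 × 0.1 / 194.4) = 0.0304
- Power = Φ(0.09/0.0304 − 1.96) = 84.1% (plan: 85%)
- ICC 0.02: design effect 1.405, effective n 166.4, power 78.1% (plan: about 80%)

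The plan's figures are reproduced to within 2 points.

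**3. Adding an assumed pair difference b** in the observed SDF arrest rate, with the variance taken at the shifted rate:

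- False non-inferiority (true SDF rate 0.81, b favours SDF): SE₁ = √([0.09 + (0.81 + b)(0.19 − b)]/194.4); probability = Φ(b/SE₁ − 1.96)
- Power (true SDF rate 0.90, b against SDF): SE₂ = √([0.09 + (0.90 − b)(0.10 + b)]/194.4); probability = Φ((0.09 − b)/SE₂ − 1.96)

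| b (points) | SE₁ | False non-inferiority | SE₂ | Power |
|---|---|---|---|---|
| 0 | 0.0354 | 2.5% | 0.0304 | 84% |
| 1 | 0.0350 | 4.7% | 0.0311 | 73% |
| 2 | 0.0345 | 8.4% | 0.0317 | 60% |
| 3 | 0.0340 | 14% | 0.0323 | 46% |
| 5 | 0.0329 | 33% | 0.0335 | 22% |

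Solving the same formulas: 1.1 points doubles the 2.5% error, 2.7 points brings power to 50%, and 3.3 points halves it to 42%.

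**4. The enlarged trial.** The Protocol Summary has 22 sites "plus an additional 11 housing facilities to address some delays in recruitment", while Section 4.2 says "The additional 4 sites will also be randomized to Arm 1 and Arm 2 for a total of 13 sites in each arm". With 590 participants, n = 295 × 0.85 = 250.75 per arm. The design effect is 1.183 with 26 sites and 1.142 with 33 (arms assumed equal), so effective n is 212.0 or 219.6. At 5 points, false non-inferiority is 35% or 37%; power falls from 87% to 24%, or from 88% to 25%. More participants do not reduce the bias.

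**5. Per lesion to person.** With L independent lesions and 90% person-level arrest, per-lesion p = 0.9^(1/L). A 1-point per-lesion difference becomes 0.9 − (p − 0.01)^L = 1.0, 1.9, 2.8 or 3.6 points for L = 1 to 4. The lesion counts are assumed, and independence makes this an upper bound.

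**6. What crossing achieves.** With 11 sites per arm the best split is 6/5 against 5/6, an imbalance of 6/11 − 5/11 = 0.091. A 5-point pair difference then leaves 0.45 points, and the step 3 formula gives 3.4% false non-inferiority. A pair covariate would inflate the variance by 1/(1 − 0.091²) = 1.008.

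**The case against.** The strongest reply is that Section 5.4.2 need not mean a fixed pair per arm. Its baseline sentence uses the singular for the facility, treatment is revealed only after the exam, and hygienists are said to arrive unaware. All three fit a scheme in which pairs alternate between arms site by site, and the own-work aim needs only a swap within each site. This stands as an alternative reading. But the 6-month sentence directs pairs by arm and in the plural, and no sentence states a site-by-site rule. A reader might infer that the arrest comparison is in fact confounded. The documents do not support that: they show what the text prescribes, not how visits were staffed.

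Safeguards also count. Section 13.2.1 provides a 4-day ICDAS calibration and withholds baseline results at follow-up. The temporary COVID-19 procedures in Section 7 include a dentist's check of charting, though the dentist may be absent at week 52. The training protocol with reproducibility details is not in the documents, so the true pair difference may be small. These measures can shrink a difference; they do not unlink it from arm.

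The 20% re-examinations are the best resource, since one reference examiner can span both pairs. Used only at week 52 and at person level, they give 0.2 × 467.5/2 = 46.75 participants per pair. With 5% to 15% discordant scores (assumed, clustering ignored), the half-width is 1.96 × √(2d/46.75), or 9 to 16 points. Lesion-level data and other follow-up visits could do better.

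Finally, version 14.0 is dated April 2023 and refers to sites where enrolment was completed, so reallocation can reach only the visits that remain.

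**Conclusion.** The concern holds as a conditional one. The allocation as written aliases examiner pair with arm for week-52 caries arrest, a primary outcome, and for new decay, and it contradicts the section's own masking sentence. Tooth pain and quality of life are self-reported and not affected.

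The sizes rest on assumed pair differences of 1 to 5 points, the plan's own sample-size inputs and a normal approximation. Their use is to show how little is needed: about 1 point doubles the one-sided error. They are not estimates of bias in this trial.

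A reader might also infer that crossing pairs would mask the week-52 examiners. It would not. Treatment is given at baseline and week 26 (Section 6.11), so with the swap both pairs will have treated at every site, and SDF colour change and restorations are visible. For the same reason neither pair is free of its own work at week 52. Crossing removes the examiner-by-arm confounding and nothing more.

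**What to change.** **Section 5.4.2**

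- (a) State which pair goes to which facilities at each visit, and reconcile this with the masking sentence. If a site-by-site scheme was used, saying so and reporting the pair-by-arm split settles the confounding question.
- (b) For any remaining visits, allocate pairs so that each covers about half of the sites in each arm. State that this neither masks examiners at week 52 nor by itself meets the own-work aim there.

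**Section 11.4**

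- (c) Add examiner pair to the week-52 arrest and new-decay models only if pairs were crossed with arm, and report the share of exams crossed. If a share c is crossed, the arm-pair correlation is 1 − c and the variance inflation is 1/(1 − (1 − c)²): 2.29, 1.33 or 1.07 for 25%, 50% or 75%. Adjusted power, Φ(0.09/(0.0304 × √inflation) − 1.96), is then 50%, 73% or 82%.
- (d) For exams already done under an arm-aligned scheme, pre-specify a sensitivity analysis that estimates the pair scoring difference, with its confidence interval, from the existing 20% re-examinations. Use lesion-level data and all follow-up visits where available. State the confounding as a limitation.

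**Cost.** Slightly more scheduling, and an examiner ID field in the analysis data if it is not already there; forms are already signed by the staff who collect the data (Section 12). No extra staff or visits are needed, since both pairs already work in both arms.

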## 6.11 Administration of Procedural Intervention

Arm 1(SDF): SDF will be administered by a licensed dental hygienist at the baseline visit, and the 26-week visit.

Arm 2(ART +FV): ART will be administered by a licensed dental hygienist at the baseline visit + Fluoride Varnish application at baseline and the 26-week visit. If ART requires scooping out the decay then a licensed dentist will scoop the decay and then have the hygienist complete the ART intervention. *For 52 week follow-up visits, where treatment will not be delivered, the study dentist may not be present.*

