## **7.2 26-Week Visit (T26) (Day 168 to Day 196)**

### **Dental Exam and Treatment**

- Dentists will administer the Safety Questionnaire (Pre-Exam).

- Hygienists will perform dental examination at participant's respective housing facility to evaluate caries arrest and identify new decay.
- Study staff will record results of dental examination.
- Hygienists, under the direction of the study dentist, will administer the intervention treatment (based on study arm) for all previously treated lesions and newly identified active root or coronal carious lesion with ICDAS-II lesion severity code of 3 or greater.
- Study staff will give participants referral sheets with exam results and direction to follow up with their personal dentist for routine dental care.
- If a participant reports any issue with the applied treatment within one week of the treatment date, the study team will return to the housing facility to examine and correct the treated tooth as needed. Within 48 hours, the study team will call the participant to ask the participant if the issue has been resolved and will administer a paper safety questionnaire. The completed paper safety questionnaire will be stored in the CRF folder and documentation of the return visit/treatment will be added to the participant's electronic record.

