### **7.3 52-Week Visit (T52) (Day 365 to 379)**

#### **Dental Exam and Treatment**

- Dentists *or* hygienists will administer the Safety Questionnaire (Pre-Exam).
- Hygienists will perform dental examination at participant's respective housing facility to evaluate caries arrest and new decay.
- Study staff will record results of dental examination.
- Study staff will give participants referral sheets with exam results and direction to follow up with their personal dentist for further treatment or routine dental care.

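### The hygienist rotation separates treater from examiner only at week 26; at the deciding 52-week exam the examining pair has already treated at that site

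*Combined protocol and SAP*

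**What the plan says.** Section 5.4.2 describes four hygienists working as two pairs. For baseline: "Two hygienists will go to the housing facility randomized to the SDF arm and the other two will go to the ART" + FV arm. At 6 months "the two hygienists that applied SDF will now go to the facilities randomized to the ART + FV facilities and vice-versa", and they go there "to conduct the 6-month follow up caries assessment exam and treatment". For the last visit the section says only: "We will follow similarly for the 12-month follow-up visit". It then draws its conclusion for the strategy as a whole, with no limit to a particular visit: "By this strategy, we will make sure that potential bias of the hygienist evaluating their own work is minimized".

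Treatment is given on two occasions. Section 6.11 states for Arm 1 that "SDF will be administered by a licensed dental hygienist at the baseline visit, and the 26-week visit"; for Arm 2 it places ART at baseline and varnish at baseline and 26 weeks. Section 7.2 says that at week 26 the hygienists "will administer the intervention treatment (based on study arm) for all previously treated lesions and newly identified active root or coronal carious lesion". At week 52 no treatment is given, and hygienists examine "to evaluate caries arrest and new decay" (section 7.3). Sections 4 and 11.1 set the primary non-inferiority hypothesis at 12 months.

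Two other safeguards are stated. Hygienists do not see the baseline findings at the 26- and 52-week exams (section 13.2.1), and a random 20% of participants are re-examined as a periodic quality check (section 5.4.2).

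**The concern.** A rotation of two pairs can keep treater and examiner apart at one follow-up visit. Once the second pair has examined and treated at a site, no pair is left that has not treated there, and the plan names no third pair or independent examiner. The safeguard therefore works at week 26 and lapses at week 52, the visit on which the primary caries-arrest comparison rests.

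Arrest is a clinical judgement made by eye and probe. An examiner who is lenient toward work done by herself or her pair would score some failures as arrested. In a non-inferiority comparison that can move the chance of a false claim up or down, depending on which arm the leniency reaches. Meanwhile section 5.4.2 tells a reader that the issue has been dealt with.

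**Working it through.** **Who treats and who examines.** Call the pair that goes to SDF sites at baseline A and the other pair B. 'Similarly' in section 5.4.2 can mean swapping back or keeping the week-26 posting.

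| Visit | SDF sites | ART + FV sites |
|---|---|---|
| Baseline, treats | A | B |
| Week 26, examines and treats | B (not yet treated there) | A (not yet treated there) |
| Week 52, if swapping back | A (treated at baseline) | B (placed ART at baseline) |
| Week 52, if staying | B (treated at week 26) | A (treated at week 26) |

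The examining pair has already treated at the site in 0 of 2 arms at week 26 and in 2 of 2 arms at week 52, on either reading.

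Three limits apply.
- The table is at pair level. The documents do not say which member of a pair treats or examines a given participant.
- About 40 participants missed the week-26 visit and treatment (section 4.2, COVID-19 modifications). For them only the baseline pair has treated, so under 'stay' they would be scored by a pair that had not treated them.
- Under 'stay' at ART + FV sites, pair A applied varnish to all teeth (section 6.7) and treated new lesions. Whether it also re-treated the baseline restorations depends on section 7.2 (all previously treated lesions) against section 6.11 (ART at baseline). Those two passages must be reconciled.

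**Illustrative size.** Inputs from section 11.2: 275 per arm, 25 per site, 15% dropout, ICC 0.01, arrest rate 90%, margin 0.09, one-sided 0.025. Analysed per arm: 275 × 0.85 = 233.75, about 234. Analysed per site: 25 × 0.85 = 21.25. Design effect: 1 + (21.25 − 1) × 0.01 = 1.2025, about 1.20. Effective n per arm: 234 / 1.20 = 195.

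The plan's own figure first. With 90% in both arms, SE = √(2 × 0.9 × 0.1 / 195) = 0.0304 and power = Φ(0.09 / 0.0304 − 1.96) = 84%, against the stated 85%. The inputs are close enough to use.

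Now put the true difference at the margin (ART + FV 90%, SDF 81%), and let a share s of failures in an affected arm be scored as arrested. This share is an assumption; the documents give no figure for it.
- Scored rate: p* = p + (1 − p)s
- Scored difference: D = p*(SDF) − p*(ART)
- SE = √{[p*(SDF)(1 − p*(SDF)) + p*(ART)(1 − p*(ART))] / 195}
- Chance of a false claim: Φ((D + 0.09) / SE − 1.96)

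| Leniency | SDF | ART | D | SE | False non-inferiority |
|---|---|---|---|---|---|
| None | 0.810 | 0.900 | −0.090 | 0.0354 | 2.5% |
| Both arms, 10% | 0.829 | 0.910 | −0.081 | 0.0339 | 4.5% |
| Both arms, 20% | 0.848 | 0.920 | −0.072 | 0.0322 | 8.1% |
| SDF only, 10% | 0.829 | 0.900 | −0.071 | 0.0345 | 7.9% |
| SDF only, 20% | 0.848 | 0.900 | −0.052 | 0.0335 | 20.4% |
| ART only, 10% | 0.810 | 0.910 | −0.100 | 0.0348 | 1.2% |
| ART only, 20% | 0.810 | 0.920 | −0.110 | 0.0342 | 0.5% |

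**The case against.** The plan claims that this bias is minimized, not removed, and the rotation does not stand alone. Examiners are calibrated by a gold standard examiner, baseline findings are withheld at both follow-up exams, and 20% of participants are re-examined. These measures stand as mitigation. They do not change who scores the outcome at week 52: withholding earlier scores does not alter who examines, and nothing ties the re-examination to week 52 or says that it supplies the outcome.

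A reader might infer that every hygienist scores lesions she treated herself. The documents do not support that. Two hygienists attend each site and an examiner may be scoring her partner's work. Under 'stay', the ART restorations placed at baseline are scored by the pair that did not place them.

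A reader might also infer that the lapse favours SDF, or take 20.4% as its size. That is not established either. If the pairs swap back, the week-52 pair is the one that placed the ART restorations, while SDF lesions were treated by both pairs. Leniency could then fall more on ART and work against the non-inferiority claim. The 20.4% needs the 'stay' reading, a 20% leniency rate, none at all for ART and a true deficit exactly at the margin.

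**Conclusion.** The concern holds as a pair-level design point: the separation that section 5.4.2 relies on exists at week 26 and not at week 52, on either reading of 'similarly'. This follows from the visit plan alone and needs no assumed figure.

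The consequence for the caries-arrest conclusion is of uncertain direction. Across the scenarios shown, the chance of a false non-inferiority claim runs from 0.5% to 20.4% against a nominal 2.5%, and the figures depend wholly on the assumed leniency and on which arm it reaches. They show that the result is sensitive to examiner leniency; they do not estimate a bias. The point should be addressed because it touches a primary outcome at its deciding visit and the repair is small.

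**What to change.** In section 5.4.2:
1. State which pair goes where at week 52, in place of 'similarly'.
2. Name one treating hygienist per pair at each site. After week 26 two of the four have treated there and two have not.
3. Assign the week-52 caries exam to one of the existing hygienists who has not treated participants at that site. The week-26 separation is kept.
4. Limit the statement about evaluating one's own work to the visits where it is true.

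The version history (version 14.0) indicates that enrolment was complete at the sites then added, so baseline postings may no longer be open to change. Where visits are already done, apply step 3 to the remaining week-52 exams, using the treatment log listed in Figure 15.3.1. This requires that the log identifies the treating hygienist, which the documents do not state. If both members of both pairs have treated at a site, say so and report it as a limitation.

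Cost: a paragraph of wording and a rota, with no added staff or visits. Clinic days with a single treater run slower. The alternative, with the same pair at baseline and week 26 and the other pair at week 52, works only for sites not yet started. It also gives up the week-26 separation, and week 26 enters the repeated-measures analysis in section 11.4.
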